8.7.5 Exploratory Endpoint Analysis

The mean change in RosaQoL subscale scores from Baseline to Week 12 will be summarized using descriptive statistics.

The subscores for the RosaQoL are computed as follows:

Total Score: the unweighted mean of all RosaQoL questions

Symptom subscale score: the unweighted mean of the following symptom questions

My rosacea burns or stings (item #2)

My rosacea is irritated (item #6)

My rosacea makes my skin sensitive (item #9)

My skin feels bumpy (uneven, not smooth, irregular) (item #16)

My skin flushes (item #17)

My skin gets irritated easily (cosmetics, aftershaves, cleansers) (item #18)

My eyes bother me (feels dry or gritty) (item #19)

Functional subscale score: the unweighted mean of the following functional questions

I try to cover up my rosacea (with make-up) (item #13)

I avoid certain foods or drinks because of my rosacea (item #15)

I avoid certain environments (heat, humidity, cold) because of my rosacea (item #21)

Emotion subscale score: the unweighted mean of the following emotion questions

I worry that my rosacea may be serious (item #1)

I worry about getting scars from my rosacea (item #3)

I worry that my rosacea may get worse (item #4)

I worry about side effects from rosacea medications (item #5)

I am embarrassed by my rosacea (item #7)

I am frustrated by my rosacea (item #8)

I am annoyed by my rosacea (item #10)

I am bothered by the appearance of my skin (redness, blotchiness) (item #11)

My rosacea makes me feel self-conscious (item #12)

I am bothered by persistence/reoccurrence of my rosacea (item #14)

I think about my rosacea (item #20)

Each individual item should be scored as follows: 1=Never, 2=Rarely, 3=Sometimes, 4=Often, and 5=All the time. Missing data values will not be used. If a subscale has items with missing results, the subscore and the total will not be calculated.

8.8 Safety Evaluation

8.8.1 Extent of Exposure

The extent of exposure to study drug in each treatment group will be summarized by total number of days of exposure, total number of applications, number of missed applications and number and percentage of subjects who are compliant. A subject will be considered compliant with the dosing regimen if the subject applied 80% to 120% of the expected number of applications and did not miss more than 5 consecutive applications while enrolled in the study.

Days of exposure = Date of last study application – Date of first study application + 1

The total number of applications taken is as follows:

(Date of Last Application – Date of First Application + 1) – (Number of Days marked as missed applications on the CRF) + (Number of extra applications marked on the CRF)

If a subject did apply medication on the last day, the total number of applications expected is as follows:

Date Subject End Participation – Date of Baseline +1.

If the total number of applications exceeds 89 then it will be set to 89.

If a subject did not apply medication on the last day, the total number of applications expected is as follows:

Date Subject End Participation - Date of Baseline

If the total number of applications exceeds 88 then it will be set to 88.

Compliance will be calculated as a percentage as 100 times the total number of applications taken from the first application until Week 12 divided by the total number of applications expected from first application until Week 12. Subjects who discontinue study medication before Week 12 will be considered to be 0% compliant for the number of days from discontinuing study medication until Week 12.

Compliance will not be calculated for subjects who are lost to follow-up or subjects who have unknown first or last application dates.

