12.5. Precautions

The following precautions are to be taken during this study:

1. Patients should avoid contact of the study product with the eyes, mouth, and lips or on any cuts or broken skin. In case of accidental exposure, the eyes should be rinsed with plenty of water.
2. The study product should not be applied to cuts, abrasions, eczematous or sunburned skin.
3. Patients should wash hands before and after applying study product.
4. Patients should allow the treated area to completely dry for at least 30 minutes after applying the study product to avoid spreading it on other areas of the face (e.g., eyes, ears, neck, etc.) and pillow cases.
5. The study product should be spread evenly in a thin layer on each area of the face (chin, left cheek, right cheek, nose, left forehead and right forehead); excessive rubbing must be avoided.
6. The study product should not be applied more than once daily and patients should not use more than the recommended amount.
7. Patients should not wash their face more than 2 or 3 times a day.
8. Facial makeup (non-medicated) may be applied according to the patient's normal daily routine (but not prior to 30 minutes after study product application).
9. Patients should not apply moisturizers, make-up, creams, lotions, powders or any topical product they do not routinely use on their face
10. Patients should not cover the treated area with a bandage (occlusive dressing) or other types of dressing after applying the study product.
11. Patients should limit sun exposure, including sunlamps (non-prescription UV light sources); avoid tanning beds/booths/parlors and sauna while using the study product.
12. Patient should use moisturizer with SPF supplied by the Sponsor or from study-approved list product and protective apparel (e.g. wide- brimmed hat) when outdoors. Patients should wait approximately 30 minutes after study product is applied on the face before applying a sunscreen. Weather extremes, such as wind or cold, may be irritating to patients receiving treatment.
13. UVA/UVB treatments are also prohibited.
14. Patients must not wear make-up to any study visits, so as not to interfere with the evaluations. If a patient comes to his/her visits with make-up on his/her face, the patient will be allowed to wash his/her face with a non-medicated cleanser and must wait at least 30 minutes before any study evaluation is made by the Principal Investigator (PI) or Sub-Investigator (Sub-I).

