18.6. Study Product Accountability and Study Records at Sites

Upon receipt of the clinical supplies, the study staff will conduct a complete inventory of study products and assume responsibility for their storage and dispensing. In accordance with federal regulations, the Investigators must agree to keep all study products in a secure, temperature-controlled location with restricted access.

All supplies sent to the Investigators will be accounted for and in no case used in any unauthorized manner. All used and unused study product will be appropriately inventoried by the clinical site, and verified by the clinical monitor.

Study product will be weighed before dispensing and upon return and weights will be recorded on the appropriate source document and eCRF.

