8.4.4 Per-Protocol (PP) Population

All subjects in the ITT population who complete the Week 12 evaluation without noteworthy study protocol violations (i.e., any patient or investigator activity that could have possibly interfered with the therapeutic administration of the treatment or the precise evaluation of treatment efficacy) will be included in the PP population and analyzed according to the treatment group they received. The PP population will include subjects in the ITT population who do not meet any of the following criteria:

- Failed any of the inclusion/exclusion criteria;
- Have taken any interfering concomitant medications;
- Did not attend the Week 12 Visit;
- Missed more than 1 post-baseline study visit prior to Week 12;
- Have not been compliant with the dosing regimen (i.e., Patients may not miss more than five consecutive days of dosing and must take 80 to 120% of expected applications. The number of expected applications will be determined for each patient based on the length of their participation in the study);
- Out of visit window (± 4 days) at the 12-week Visit.

Subjects that discontinue from the study due to an AE related to study treatment or documented lack of treatment effect will be included in the PP population. Data for these subjects will not be imputed by multiple imputation but rather their data will be imputed with values consistent with their status as treatment failures. See Section 8.1.5 for additional detail. Prior to breaking the blind, other additional criteria may be added to the list to accommodate for unforeseen events that may occur during the conduct of the trial and result in noteworthy study protocol violations.

All efficacy analyses performed on the PP population will be according to the treatment they received.

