(Page xx of yy)

Subject	Age/Sex	Eval	Visit	Visit Date	Study Day ¹	Within Visit Window ²	Reason Screening And Baseline Occurred on Different Days	Reason for Unscheduled Visit
xxxxxx	xxxx	xxxxxxxx	xxxxxxxx	xxxxxxxx	xx	xxx		
			xxxxxxxx	xxxxxxxx	xx	xxx	xxxxxxxx xxx xx	
			xxxx x	xxxxxxxx	xx	xxx	xxxxxxxx	
			xxxx x	xxxxxxxx	xx	xxx		
			xxxx x	xxxxxxxx	xx	xxx		
			xxxx xxxxx	xxxxxxxx	xx	xxx		
xxxxxx	xxxx	xxxxxxxx	xxxxxxxx	xxxxxxxx	xx	xxx		
			xxxxxxxx	xxxxxxxx	xx	xxx		
			xxxx x	xxxxxxxx	xx	xxx		
			xxxx x	xxxxxxxx	xx	xxx		
			xxxxxxxxxxxx xxxxx xxx	xxxxxxxx	xx	xxx		xxxxxxxxxxxx
			xxxx x	xxxxxxxx	xx	xxx		
			xxxx xxxxx	xxxxxxxx	xx	xxx		
xxxxxx	xxxx	xxxxxxxx	xxxxxxxx	xxxxxxxx	xx	xxx		
			xxxxxxxx	xxxxxxxx	xx	xxx		
			xxxx x	xxx xxx	xx	xxx		xxx xxx
			xxxx x	xxx xxx	xx	xxx		xxx xxx
			xxxx x	xxxxxxxx	xx	xxx		
			xxxx xxxxx	xxxxxxxx	xx	xxx		

¹ Day is calculated as date - Baseline date for dates prior to Baseline visit. Otherwise, day is calculated as date - Baseline date + 1 for dates on or after Baseline visit.

² Determined by protocol-specified visit window for scheduled visits after Baseline.

SOURCE: USERNAME\SPONSOR\PROJECT\JOBNAME (DATE, TIME)

Listing sorted by Subject and Visit Number.

Listing 16.2.5.2: Subject Dosing Compliance
Treatment Arm
(Page xx of yy)

Subject	Age/Sex	Eval	Date of First Application	Date of Last Application	Number of Days of Exposure	Calculated ¹ Number of Applications	Amount of Study Drug Used (g)	Maximum Number of Consecutive Missed Applications	Percent Compliant	Compliant ²
xxxxxx	xxxx	xxxxxxxx	xxxxxxxxxx	xxxxxxxxxx	xx	xx	xxxx	xx	xxxxx	xxx
xxxxxx	xxxx	xxxxxxxx	xxxxxxxxxx	xxxxxxxxxx	xx	xx	xxxx	xx	xxxxx	xxx
xxxxxx	xxxx	xxxxxxxx	xxxxxxxxxx	xxxxxxxxxx	xx	xx	xxxx	xx	xxxxx	xxx
xxxxxx	xxxx	xxxxxxxx	xxxxxxxxxx	xxxxxxxxxx	xx	xx	xxxx	xx	xxxxx	xxx
xxxxxx	xxxx	xxxxxxxx	xxxxxxxxxx	xxxxxxxxxx	xx	xx	xxxx	xx	xxxxx	xxx

¹ The total number of applications was calculated using the date of first application, date of last application, and number of applied applications at a deviation.

² A subject was considered compliant with the dosing regimen if the subject did not miss more than 5 consecutive days applying and applied 80-120% of expected applications based on the length of their participation in the study.

SOURCE: USERNAME\SPONSOR\PROJECT\JOBNAME (DATE, TIME)

Listing sorted by Subject.

Listing 16.2.5.3: Subject Dosing Deviations
Treatment Arm
(Page xx of yy)

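### Extra applications offset missed days in the SAP's compliance percentage, so a patient treated on fewer than 80% of expected days can still meet the 80% dosing limit for the per-protocol population

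*SAP*

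**What the plan says.** SAP 8.8.1 (Extent of Exposure) starts from the number of days from first to last application, both included, and subtracts "Number of Days marked as missed applications on the CRF) + (Number of extra applications marked on the CRF". The footnote to Listing 16.2.5.2 describes the same kind of count: "The total number of applications was calculated using the date of first application, date of last application, and number of applied applications at a deviation".

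For a patient who applied on the last day, the denominator is "Date Subject End Participation – Date of Baseline +1". For a patient who did not, it is one day fewer. Caps of 89 and 88 apply respectively.

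A patient is compliant if he or she "applied 80% to 120% of the expected number of applications and did not miss more than 5 consecutive applications while enrolled in the study". SAP 8.4.4 uses the same two limbs as a PP criterion: "Patients may not miss more than five consecutive days of dosing and must take 80 to 120% of expected applications".

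On the dosing instruction, protocol 12.5 item 6 says: "The study product should not be applied more than once daily and patients should not use more than the recommended amount". Listing 16.2.5.3 puts dates with a non-standard number of applications under dosing deviations.

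**The concern.** A skipped day and a doubled day are both departures from once-daily use. In 8.8.1 they enter with opposite signs, so they net out, and the 80% lower limit ends up bounding missed days minus extra applications. It does not bound missed days. The five-consecutive-day rule catches long gaps only, and no written criterion limits the total number of missed days or of doubled days.

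The PP analysis repeats both co-primary analyses (SAP 8.7.1). SAP 8.4.4 intends it for patients whose treatment was not disturbed. If the written dosing criterion passes patients treated on well under 80% of days, PP does not do quite what it is described as doing, and the compliant row in Table 14.3.0.1 overstates adherence for those patients.

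**Working it through.** **Inputs.** The formulas are those of SAP 8.8.1. The Week 12 visit is Day 85 ± 4 (SAP 6.1). The limits are 80% to 120% and no more than 5 consecutive misses (SAP 8.4.4 and 8.8.1).

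**The plan's own figure.** The SAP states: "If the total number of applications exceeds 89 then it will be set to 89". Day 85 + 4 = 89 with a last-day application, and 89 − 1 = 88 without. Both caps reproduce, so the formulas are being read as intended.

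**Formula.** Compliance % = 100 × [(last − first + 1) − missed + extra] / expected.

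**Scattered misses with a few doubled days.** Visit on Day 85, no application that day, so expected = 85 − 1 = 84. Applications run from Day 1 to Day 84 (span 84), with 20 scattered missed days and 5 doubled days.
- Applications taken: 84 − 20 + 5 = 69, and 69/84 = 82.1%, so the patient meets the limit.
- Days treated: 84 − 20 = 64, and 64/84 = 76.2%, below 80%.

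**Alternate-day doubling.** Same visit, expected 84. The patient treats on Days 1, 3, ..., 83, twice each time. That is 42 treated days, span 83, 41 missed days within the span, 42 extras, and a longest gap of one day.
- Applications taken: 83 − 41 + 42 = 84, and 84/84 = 100%.
- Days treated: 42/84 = 50%.
- If Day 84 is also marked as missed, the count is 83 − 42 + 42 = 83, and 83/84 = 98.8%. The conclusion is the same.
- With a last application on Day 85: 85 − 42 + 43 = 86, and 86/85 = 101.2%, with 43/85 = 50.6% of days treated.

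**What the limit bounds.** 80% of 84 is 67.2, so at least 68 applications are needed. With a span of 84 and no extras, at most 84 − 68 = 16 days can be missed. With extras, the condition becomes missed − extra ≤ 16, so each extra application allows one more missed day.

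**Where the five-day rule does work.** Six days doubled then six days off, over 85 days, gives 86/85 = 101.2% but a six-day gap, so the patient is not compliant. One 42-day gap with the other 42 days doubled gives 84/84 = 100% and also fails. Alternate days without doubling gives 43/85 = 50.6% and fails the 80% limit. The problem is therefore confined to patients who both miss days in short gaps and record extra applications.

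**After the fix.** The two patients above score 64/84 = 76.2% and 42/84 = 50% against the lower limit, and both fail. Their totals of 82.1% and 100% remain under the 120% limit.

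**The case against.** The best defence is that the criterion counts doses. Protocol 19.1.4 and SAP 8.4.4 both set a range up to 120%, and an upper limit above 100% makes sense only if extras count. On that reading 8.8.1 implements the criterion faithfully. This is right for the upper limit, and it means the fix changes what the lower limit measures even though the figure of 80% stays. It does not explain why a floor on adherence to a once-daily product should credit applications that protocol 12.5 tells patients not to make.

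Other points on that side stand and limit the concern:

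- A reader might infer that an alternate-day doubler necessarily stays in PP. The documents do not support that. SAP 8.4.4 has a judgement-based exclusion for activity that may disturb treatment and allows criteria to be added before unblinding. SAP 8.1.9 and 8.3 provide for further major deviations to be settled before lock. Listing 16.2.5.3 would show each deviation date. What can be said is that no written criterion removes the patient.
- A reader might infer that skipping caused by irritation in the active arm would be hidden. It would not. Missed days are subtracted, and Table 14.3.0.1 summarises missed applications by arm without offsetting extras. Masking needs the same patient to skip and to double, and irritation gives no reason to double.
- A reader might infer that the pump weights are a neglected check that would expose these patients. Protocol 18.6 says only "Study product will be weighed before dispensing and upon return and weights will be recorded on the appropriate source document and eCRF", under accountability. With equal amounts per application, the alternate-day doubler's 84 applications use the same total grams as 84 single daily ones. The plan sets no gram target, and grams used are already listed by patient in Listings 16.2.5.2 and 16.2.5.4.
- Extras count only if marked on the CRF, and the visit procedures in protocol 13.12 to 13.14 mention recording missed doses only.

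**Conclusion.** The concern holds as a defect in the derived compliance variable. Extra applications cancel missed days in the 80% lower limit, so the written dosing criterion can be met by a patient treated on 76.2% of expected days, or in the extreme on 50%, provided no gap exceeds five days.

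The consequence is small. Protocol 19.3 makes PP supportive, and secondary testing uses ITT only (SAP 8.1.8 and 8.7.3), so the ITT analyses do not change. Only PP membership and the compliant yes/no row are affected.

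The worked patients are hypothetical and assume that extras are recorded on the CRF. The documents give no basis for estimating how many such patients there would be, or whether they would differ by arm. The change is worth making because it is cheap and gives the lower limit a clear meaning. Nothing here suggests bias in the primary result.

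**What to change.** Before unblinding, amend SAP 8.8.1 and 8.4.4 as follows:

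- Lower limit: 100 × [(last − first + 1) − missed days] / expected applications must be at least 80. Extras receive no credit.
- Upper limit: 100 × [(last − first + 1) − missed days + extra applications] / expected applications must be no more than 120, as now. Extras must stay inside the total here, since extras alone would almost never exceed 120% of expected.
- Add a row for the number of extra applications, by arm, to Table 14.3.0.1. Align the footnotes to Tables 14.0.2.1 and 14.3.0.1 and to Listing 16.2.5.2, and note the change in SAP section 10.

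The 80% and 120% thresholds and the five-consecutive-day rule stay as they are. This is an analysis definition only and leaves the dosing instruction untouched.

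The inputs are already planned for: 8.8.1 uses missed and extra applications from the CRF, and Listing 16.2.5.3 holds applications per deviation date. The cost is SAP wording and a few lines of programming. The downside is a few more PP exclusions and a slightly lower reported compliance rate. A by-arm summary of grams used could be added as a reporting choice, but it is optional and not part of the error.

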8.8.2 Adverse Events (AEs)

All AEs occurring during the study will be recorded and classified on the basis of MedDRA terminology. Descriptions of AEs will include the date of onset, the date the AE ended, the severity of the AE, the relationship to study product, the action taken regarding study product usage, the action taken to treat the AE, and the outcome. All reported treatment-emergent AEs (TEAEs) will be summarized by the number of patients reporting AEs, system organ class, severity, seriousness, and relationship to study product. TEAEs are those AEs with an onset on or after the date of the first study product application; if the AE is not indicated as prior to first application on the CRF then it will be considered a TEAE.

AEs will be summarized by treatment group and severity. Each patient will be counted only once within a system organ class or a preferred term by using the AEs with the highest severity within each category.

AEs will be summarized by treatment group and relationship to study product. Each patient will be counted only once within a system organ class or a preferred term by using the AEs with the greatest relationship within each category.

If relationship to study drug is reported as definitely, probably, or possible, then this is defined as related. If relationship to study drug is reported as unlikely or not related, then this is defined as unrelated.

Comparisons among treatment groups will be made by tabulating the frequency of patients with one or more AEs (classified into MedDRA terms) during the study. The Fisher's Exact test will be used to compare the proportion of patients in each treatment group who report any AE at a

significance level of 0.05. The specific system organ classes and preferred terms analyzed will be those that are reported by at least one percent of the patients in any treatment group.

All information pertaining to AEs noted during the study will be listed by patient, detailing verbatim given by the investigator, preferred term, system organ class, start date, stop date, severity, actions taken, and drug relatedness. The AE onset will also be shown relative (in number of days) to the day of initial application of the randomized study product.

Serious adverse events (SAEs) will be tabulated by patient within treatment groups.

In addition, a list of patients who discontinued from the study and a list of patients who experienced SAEs will also be provided.

